Progressive disease	Decrease of eGFR by more than 30% of baseline eGFR, or increase in UPCR determined from 24 h urine collection by more than 50% from baseline value and less than 10% decline of anti-PLA2R antibody titers compared to baseline.
Proteinuria	Proteinuria will be assessed by UPCR from 24 h urine throughout this clinical trial.
Proteinuria Responses	Proteinuria responses are reflected by the reduction of proteinuria as measured by UPCR. Based on the proteinuria responses, the following response categories are defined by this protocol (baseline proteinuria value is defined as the mean of the values determined at screening and prior to Cycle 1 Day 1 pre-dose [UPCR from 24 h urine]):
- Proteinuria complete response (Prot-CR)	Reduction of proteinuria to less than 0.5 g/g, serum albumin within the reference range and stable eGFR (at least 80% of baseline).
- Proteinuria partial response (Prot-PR)	Reduction by at least 50% of UPCR at a given visit compared to baseline, proteinuria below 3.0 g/g and stable eGFR (at least 80% of baseline), but not meeting Prot-CR.
- Overall proteinuria response (OPR)	The sum of Prot-CR and Prot-PR
Treatment emergent adverse event (TEAE)	TEAEs are defined as any adverse event reported within the following time interval: start of first administration of trial drug until date of last administration of MOR202 + 28 days
Toxicity and symptoms for adverse event reporting and medical history are graded according to the National Cancer Institute Common Terminology Criteria for Adverse Events, version 5.0 (NCI-CTCAE 5.0) throughout this Clinical Trial Protocol unless otherwise stated. A copy will be provided in the Investigator Site File.	

## 4. INTRODUCTION

The purpose of the trial is to assess safety and efficacy of the human anti-CD38 antibody MOR202 (compound MOR03087) in subjects with anti-PLA2R antibody positive membranous nephropathy (aMN) eligible for immunosuppressive therapy (IST) or who have failed to respond to previous IST.

Membranous nephropathy (MN) is the leading cause of nephrotic syndrome (NS) in adults (Medawar et al 1990). About 80% of MN cases are idiopathic, 20% are related to other diseases or exposures (Couser et al 2017). The overall global incidence is estimated at 1.2 per 100,000 per year (Mc Grogan et al 2011).

Although up to 30% of patients experience spontaneous remissions, and although the disease usually progresses slowly, approximately 30% to 40% of patients eventually develop end-stage renal disease (ESRD) (Ruggenenti et al 2003, Troyanov et al 2004). Patients with MN remaining nephrotic are at increased risk for thromboembolic (Wagoner et al 1983) and cardiovascular events (Lee et al 2016). Currently, there is no approved standard treatment for MN and there is no predictive test available that identifies patients who will undergo spontaneous remission. The current treatment regimen mainly comprises off-label use of various non-immunosuppressive and immunosuppressive drugs (Couser et al 2017, Bomback et al 2018).

Commonly, patients presenting with proteinuria and an established (histological) diagnosis of MN receive supportive, non-immunosuppressive therapy. Typically, this consists of a combination of angiotensin converting enzyme inhibitors (ACEIs) or angiotensin receptor blockers (ARBs), statins and diuretics. Evidence of a direct therapeutic effect of ACEIs and/or ARBs either immunologically or on proteinuria directly is lacking, particularly in light of the aforementioned underlying rate of spontaneous remissions.

Should supportive therapy not lead to reduction of proteinuria within months, treatment is escalated by employing IST with the most common IST regimens being cyclophosphamide combined with steroids, calcineurin inhibitors (CNIs: cyclosporine [CSA] or tacrolimus), mycophenolate-mofetil (MMF) or rituximab (RTX). To a lesser extent, adrenocorticotropic hormone (ACTH) has been used. Treatment effects of these combinations appear to be similar: remission of proteinuria can be expected in about 50 to 60% of patients in the first year and 70 to 80% at 2 to 3 years (Couser et al 2017).

Out of all patients with primary MN not receiving IST, 30% to 40% progress to ESRD in 10 years after disease onset. IST reduces the progression rate to 10% or less (Bomback et al 2018). Relapses in proteinuria are seen in about 25% of patients previously treated with IST. The cases are usually re-treated with a different IST combinations (Couser et al 2017, Bomback et al 2018).

Autoantibodies binding to the PLA2R antigen are highly specific to primary MN. They are present in approximately 70% of patients diagnosed with this condition (Beck et al 2009). It is clinically observed that anti-PLA2R antibody titers correlate tightly with disease activity (Bomback et al 2018). Taken together with the fact that the disease defining glomerular basement changes contain both PLA2R protein as well as antibody complex deposits, indirect evidence is provided that indeed anti-PLA2R antibodies play a causative role in MN. This in consequence currently leads to a change of previously established therapy algorithms, i.e. to an IST guided by anti-PLA2R titers in patients where these antibodies are detectable. Nowadays, patients with elevated

circulating levels of anti-PLA2R antibodies and proteinuria >3.5 g per day are candidates for early IST (Couser et al 2017, Bomback et al 2018, Vriese et al 2017).

The above described ISTs exhibit considerable toxicity: 25% of patients treated with cyclophosphamide demonstrate adverse events (AEs) such as infections, infertility, hematologic toxicity and malignancy later in life (Couser et al 2017). Disadvantages of CNIs include long-term nephrotoxicity, the need to closely monitor drug levels and the increased risk for hypertension and diabetes. Relapse rates with CNIs seem to be higher than with cyclophosphamide [40 to 50 % versus 25%] (Cattran and Brenchley 2017, Tran et al 2015, van de Logt et al 2016).

Therapy with RTX, an anti-CD20 therapeutic antibody, allows for a more targeted IST approach by depleting B cell populations involved in producing autoantibodies. RTX response rates seem to be similar to alkylating agents and CNIs, whereas side effects seem to be less than for other drugs used in IST (Ruggenti et al 2012, Fervenza et al 2017, Fervenza et al 2015). A prospective randomized trial testing RTX versus Cyclosporin A found RTX to be non-inferior (Fervenza et al 2017).

Interestingly, CD20 is not expressed on mature antibody producing plasma cells, the main source of endogenous immunoglobulins. Indeed, a variable but essential amount of the circulating antiPLA2R antibodies may be produced by a mature, long-lived plasma cell pool with a CD20 negative but CD38 positive immunophenotype. Residual long-lived plasma cells could be a possible explanation for RTX non-responders as well as data indicating a trend towards lower response rate of RTX in MN for subjects with high anti-PLA2R antibody titers (Ruggenti et al 2012, van de Logt et al 2018).

[figure not shown]
Thus, an anti-CD38 directed specific plasma cell depletion by MOR202 may provide a viable emerging therapeutic option sparing patients of significant toxicity of broader acting immunosuppressive agents, possibly effective in patients with limited benefit of an anti-CD20 directed therapy.

#### 4.1. Background - nonclinical studies

CCI

[figure not shown]
CCI

#### 4.1.3. Toxicology

Based on the high sequence identity between marmoset monkey and human CD38 protein, the comparable binding affinity and expression levels of CD38 on blood cells as well as the similar activity to induce ADCC by PBMCs, the marmoset monkey was selected as the relevant species for the non-clinical safety assessment of MOR202.

CCI

**CCI**

## 4.2. Background - clinical studies

To date, MOR202 has been administered in the first-in-human (FIH) study MOR202C101 in 91 subjects with MM. This study is a combined dose escalation and dose confirmation study with a maximum dose of 16 mg/kg administered i.v. once weekly (including a loading dose on Cycle 1, Day 4). MOR202 was applied either as a single agent or in combination with dexamethasone (DEX), lenalidomide (LEN)/DEX or pomalidomide (POM)/DEX. The overall treatment duration was based on clinical response with a continuous treatment for up to 3 years. The maximum tolerated dose (MTD) was not reached in this trial and the recommended dose was defined at 16 mg/kg once weekly (i.e. the highest dose tested). As of 30-Nov-2019, 21 subjects were treated at this dose level for more than 6 months (13 subjects for more than 12 months and 9 subjects for more than 24 months) (Jarutat 2018, Raab et al 2020). **CCI**

### 4.2.1. Clinical pharmacokinetics and immunogenicity

The PK of MOR202 administered i.v. to MM patients has been well characterized by a 2-compartment population PK model. The volume of distribution was found to be increased at lower MOR202 doses most likely reflecting the impact of target-mediated drug disposition (TMDD) effects. So far, anti-drug antibody (ADA) samples from 85 MM subjects with a treatment duration up to a maximum of 3 years have been analyzed. No ADA has been detected to date.

### 4.2.2. Clinical safety

The most commonly reported treatment-emergent adverse events (TEAEs) in the FIH study (MOR202C101) in MM were hematological AEs, such as lymphocytopenia, leukocytopenia, thrombocytopenia, and anemia.

The combination drugs for MM used in the FIH study are intrinsically myelosuppressive when administered as single agents. Anti-CD38 monoclonal antibodies (mAbs) may further deteriorate cytopenias induced by such background therapy. Cytopenic effects are well known and manageable via treatment with colony stimulating factors and blood transfusions.

**CCI**

Non-hematological TEAEs related to MOR202 reported in more than 5% of subjects overall in the FIH study were fatigue, infusion-related reactions, respiratory and urinary tract infections, diarrhea, nausea, hypokalemia, C-reactive protein increased, cough, constipation, hypophosphatemia, pyrexia, nasopharyngitis, and oral herpes.

Please refer to the Investigator Brochure for MOR202 for further details.

### 4.2.3. Clinical efficacy

In the MM studies, MOR202 has demonstrated clinical activity comparable to other CD38 targeting agents in MM in terms of overall response rates (Raab et al 2020). CCI

### 4.2.4. Other anti-CD38 antibodies

Daratumumab and isatuximab have been approved for the therapy of different types of MM. TAK-079 is currently in mid stage clinical development for MM, systemic lupus erythematosus (SLE), myasthenia gravis and immune thrombocytopenic purpura.

[figure not shown]
There is no information available, whether these compounds were tested in patients with MN.

## 5. ~~CLINICAL TRIAL PURPOSE AND OBJECTIVES~~

The purpose of the trial is to assess the safety and efficacy of the human anti-CD38 antibody MOR202 in subjects with aMN in two cohorts with subjects:

- Presenting with medium/high anti-PLA2R titer either newly diagnosed or after relapse and eligible for IST (Cohort 1) or
- With aMN refractory to IST (Cohort 2).

	Objective	Endpoint
Primary	To assess the safety and tolerability of MOR202 treatment in subjects with aMN.	Incidence and severity of TEAEs.
Key Secondary	To assess the effect of MOR202 on serum antiPLA2R antibodies in subjects with aMN.	Best immunological response: rate of sICR, ICR and IPR based on reduction of serum anti-PLA2R antibody titer.
Secondary	To assess the immunogenicity of MOR202 (anti-MOR202 antibody formation) in subjects with aMN.	Number and antibody titers of subjects tested positive for anti-MOR202 antibodies.
	To assess the PK profile of MOR202 in subjects with aMN.	MOR202 serum concentrations after multiple i.v. administrations.
	To assess the safety in subjects with aMN after MOR202 treatment and during the follow-up phase.	Incidence and severity of AEs in the follow-up phase.
Exploratory	CCI	

	
CCI
 
	
Additional exploratory analyses may be performed to characterize further potential pharmacodynamic biomarkers under MOR202 treatment.
 
CCI
 

• Changes in peripheral blood immune cell populations.

 
CCI
 

## **6. CLINICAL TRIAL DESIGN**

### **6.1. Rationale**

#### **6.1.1. Rationale for this Clinical Trial**

This trial primarily seeks to assess the safety and tolerability of MOR202 therapy in aMN subjects. As a key further objective, the immunological response under MOR202 therapy will be assessed. Reduction in proteinuria as an early clinical efficacy parameter will be measured as well.

The monoclonal anti-CD38 antibody MOR202 selectively binds to the CD38 antigen and thereby depletes antibody producing cells such as plasmablasts and plasma cells mainly via ADCC and ADCP.

Plasma cells and plasmablasts are the source of pathogenic anti-PLA2R antibodies. Published evidence shows a tight correlation of the clinical course of MN with PLA2R autoantibody titers: high titers and sustained or re-emerging positivity of anti-PLA2R antibody titers during therapy have been demonstrated as negative predictors for outcome. Here, MOR202's mode of action provides a compelling rationale for hard-to-treat aMN subjects, i.e. those presenting with high autoantibody titers, or subjects with insufficient immunological response to prior therapy.

#### **6.1.2. Dosing Rationale**

CCI

CCI

## 6.2. Overall Clinical Trial Design and Investigational Plan

This phase Ib/IIa multicenter trial enrolls subjects with anti-PLA2R antibody positive membranous nephropathy (aMN) indicated for IST into two cohorts:

Cohort 1 will consist of approximately 20 aMN newly diagnosed or relapsing subjects stable on supportive care treatment with ACEI/ARB at screening with proteinuria and medium/high serum titers of anti-PLA2R antibodies eligible for IST. (Note: Patients in France will not be enrolled in Cohort 1.)

Cohort 2 will consist of approximately 10 subjects with aMN refractory to IST and requiring other forms of IST.

[figure not shown]
For detailed description of the subjects in Cohort 1 and 2 and the respective in- and exclusion criteria refer to [Section 7.1](#) and [Section 7.2](#).

The trial design includes a Safety Run-in, which in the initial stage of the trial intends to limit drug exposure to the first three subjects (see [Section 6.3](#)). The remainder of planned subjects may only start treatment contingent on a positive outcome of the safety observations in these initial three subjects.

All trial subjects, including the safety run-in subjects, will follow the clinical trial schedule (Figure 1) consisting of a

- Screening Phase
- Treatment Phase
- Follow-up Phase

**Figure 1 Clinical Trial Schedule**

### 6.3. Safety Run-in

As this is the first time that MOR202 is tested in subjects with aMN, a safety-run-in is planned.

The safety run-in period consists of the following:

The first three subjects dosed in this trial (regardless of cohort) will be treated and observed until C2D1 or until they have demonstrated a toxicity leading to discontinuation of treatment, whichever is earlier. In order to ensure sufficient exposure of three safety run-in subjects to MOR202, subjects will be replaced if within their first treatment cycle (C1) they

- Missed more than two doses of MOR202, or
- Discontinued treatment for reasons other than toxicities.

The safety run-in continues until three subjects are treated with sufficient exposure to MOR202. Replaced subjects may remain on trial and continue trial treatment as per protocol.

After the safety run-in, further subjects may start treatment unless any grade 4/5 ADR (related to MOR202) has occurred. If a grade 4/5 ADR occurs during the safety run-in, then a safety review must take place and start of treatment for further subjects will be contingent on the safety review outcome. The safety review will consist of an evaluation based on the number and type of all AEs occurring during the first cycle and laboratory values (biochemistry and hematology) and will be

performed by representatives of the participating investigators and the sponsor (Safety Review Panel) as defined in a respective charter. The safety review will be held after C2D1 of the third subject.

The outcome of this safety review will also provide a confirmation on the dose and dosing schedule for MOR202 or recommendation for an adapted dose and/or dosing schedule to be used in the following part of the trial or recommendation for termination of the trial because of unacceptable toxicity. Safety run-in subjects will continue the trial as per protocol during the safety review. Afterwards, their MOR202 dose may be altered as well.

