Immunogenicity	
The presence of potential anti-drug antibodies and corresponding titers will be assessed at selected time points for all subjects treated with MOR202 during the course of the trial.

Biomarker Assessments	
At selected time points assessments may include:
 
Peripheral blood immune cell populations CCI [REDACTED]
 
Serum concentrations of antigen specific antibodies (e.g. anti-tetanus toxoid titer), CCI [REDACTED]
 
CCI [REDACTED]

Safety run-in
	
The safety run-in period consists of the following:
 
The first three subjects dosed in this trial (regardless of cohort) will be treated and observed until Cycle 2, Day 1 (C2D1) or until they demonstrate a toxicity leading to discontinuation of treatment, whichever is earlier.
 
Treatment initiation of further subjects will be paused and re-started after completion of the safety run-in period, unless any grade 4/5 adverse drug reaction (ADR) (i.e. AE at least suspected to be possibly related to MOR202) occurs.
 
If a MOR202 related grade 4/5 ADR occurs, then a safety review must take place and treatment initiation for further patients will be contingent on safety review outcome. Subjects involved in the safety run-in will continue the trial as per protocol. The safety review consists of an evaluation based on the number and type of AEs occurring during the first cycle as well as laboratory values (biochemistry and hematology). It will entail a recommendation either to keep the current dose of MOR202 or to adapt the dose for the remainder of the trial or to terminate the trial because of unacceptable toxicity. The evaluation will be performed within two weeks after completion of the safety run-in phase.

Statistical Methods and Data Analysis
	
All data in this Phase Ib/IIa trial will be summarized descriptively using appropriate tabular overviews. Summary statistics for continuous variables will include number of subjects, mean, median, Q1, Q3, standard deviation, minimum, and maximum. For categorical variables, frequencies and percentages will be provided. When required for the analysis of a particular variable, the baseline value will be the last recorded value prior to first treatment. For trial endpoints point estimates and 95% confidence limits will be presented. Time-to-event endpoints will be analyzed using the Kaplan-Meier methodology. No formal statistical hypothesis testing will be performed.

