### 8.7. Treatment management of subjects with toxicity

For the first dosing of MOR202, subjects should exhibit hemoglobin, leucocyte, neutrophil and platelet counts meeting the eligibility criteria. They should not have an active infection  $\geq$  grade 2.

For subsequent doses, in case a subject shows laboratory values as listed below, further treatment of the subject has to be interrupted:

- Hemoglobin level < 60 g/L (grade 3): interruption until resolved to  $\geq 80$  g/L.
- Platelet count <  $75.0 \times 10^9/L$  (grade 2): interruption until resolved to  $\geq 100.0 \times 10^9/L$ .
- Neutrophil count <  $1.000 \times 10^9/L$  (grade 3): interruption until resolved to  $\geq 1.500 \times 10^9/L$ .

If the subject exhibits any other clinically relevant adverse drug reaction  $\geq$  grade 3, MOR202 administration has to be interrupted until the toxicity has resolved to grade 2 or better.

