## **9. TRIAL PAUSING OR TERMINATION**

### **9.1. Safety Review Triggers and Decision Making**

After completion of the safety run-in, toxicities leading to discontinuation will be continuously monitored. Recruitment into the MOR202C103 clinical trial will be paused in the following situation until a safety review by the Safety Review Panel consisting of representatives of the participating investigators and the sponsor (as defined in [Section 6.3](#)) is performed:

- If at any time treatment with MOR202 had to be discontinued due to the reasons listed in [Section 8.8.1](#) in at least 2 subjects treated.

The safety review will consist of an evaluation based on the number and type of AEs and laboratory values (biochemistry and hematology) and will be performed by representatives of the participating investigators and the sponsor as defined in a respective charter. Based on the assessment, the Safety Review Panel (see [Section 6.3](#)) will decide on further steps, e.g. pause of dosing in all subjects, introduction of any required protocol changes or trial termination due to unacceptable toxicity.

Additional safety review may be triggered at any time if any of the following occur:

- Thrombocytopenia  $\geq$  grade 3 in at least 4 subjects
- IRR  $\geq$  grade 3 in at least 4 subjects
- A single patient is not recovering to  $\leq$  grade 2 from  $\geq$  grade 3 ADRs related to MOR202 within 21 days despite adequate treatment of the ADR.

The Safety Review Panel will convene, perform a safety review and make recommendations as outlined above.

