#### **10.8.10. Reporting of AEs, SAEs and AESIs**

All AEs and SAEs will be collected from the signing of the ICF until the EOS visit. For screening failure patients only SAEs will be collected.

All SAEs and AESI must be reported to IQVIA Pharmacovigilance within 24 hours of investigator awareness. The investigator will submit any updated (follow-up) SAE data within 24 hours of investigator awareness.

Investigators are not obligated to actively seek AEs or SAEs after conclusion of the study participation. However, if the investigator learns of any SAE, including AEs resulting in death, at any time after a participant has been discontinued from the study, and he/she considers the event to be reasonably related to the study intervention or study participation, the investigator must promptly notify IQVIA Pharmacovigilance.

All AEs, including SAEs will be reported in eCRF. SAEs and AESIs will automatically be transmitted to IQVIA Pharmacovigilance via the eCRF. If the eCRF is not available, a paper SAE Report Form should be sent to IQVIA Pharmacovigilance via email or fax or the Investigator should call the IQVIA SAE hotline within 24 hours of being made aware of the SAE/AESI. When the eCRF system becomes available again, the SAE/AESI information must be entered as soon as possible of the system becoming available. Refer for contact information to the site reference manual for contact details.

The sponsor or designee will report all SAEs to local health authorities, Independent Ethics Committees (IECs) or Institutional/Independent Review Boards (IRBs) and investigators as required by local regulations.

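### A grade 4/5 drug reaction in the first or second run-in subject neither brings the mandatory safety review forward nor holds the first dose of run-in subjects not yet started

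*Protocol*

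**What the plan says.** The run-in exists because this is the first use of MOR202 in this disease. Protocol section 6.2 says that it "intends to limit drug exposure to the first three subjects". Each of the three is observed to C2D1, or to a toxicity that ends treatment if that comes first.

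One grade 4/5 reaction related to MOR202 makes a panel review compulsory (section 6.3). Three places give its timing:

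- Protocol 6.3: "The safety review will be held after C2D1 of the third subject".
- SAP 6.4.1: the same rule.
- Synopsis: "The evaluation will be performed within two weeks after completion of the safety run-in phase".

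Until the review reports, *further subjects* may not start. For the run-in subjects themselves, section 6.3 says: "Safety run-in subjects will continue the trial as per protocol during the safety review". The synopsis agrees.

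The rules for pausing the trial are in section 9.1, which opens: "After completion of the safety run-in, toxicities leading to discontinuation will be continuously monitored".

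**The concern.** A run-in should contain exposure until someone has judged the early toxicity. This one does so for the fourth subject onward. It does not do so within the run-in. If subject 1 has a life-threatening or fatal reaction, the protocol as written lets subjects 2 and 3 start and be dosed weekly through Cycle 1, and only then requires the panel to consider dose, schedule or termination. What is at stake is the exposure of one or two patients to a regimen that has just triggered the trial's own mandatory review.

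**Working it through.** The plan gives no figure on this point, so there is none to reproduce. The check has four parts.

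**1. Whom the hold covers.** Section 6.3 lets *further subjects* start after the run-in. Section 6.2 speaks of the planned subjects beyond the initial three. The synopsis pauses *further subjects* until the run-in is complete. All three mean subject 4 onward. Reading subjects 2 and 3 into the hold would be circular, because the review that would release them waits for subject 3's C2D1.

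**2. Whether another rule fills the gap.**

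| Provision | Convenes the panel earlier? | Holds another run-in subject's first dose? |
|---|---|---|
| 8.7: "MOR202 administration has to be interrupted until the toxicity has resolved to grade 2 or better" | No | No; affected subject only |
| 8.3.1 and 8.8.1: permanent stop, e.g. after a grade 4 infusion reaction | No | No; affected subject only |
| 10.8.10: "All SAEs and AESI must be reported to IQVIA Pharmacovigilance within 24 hours of investigator awareness" | No; informs pharmacovigilance | No |
| 9.1, mandatory pause | Needs discontinuations in at least 2 subjects | Pauses recruitment; introduced as a post-run-in rule |
| 9.1: "Additional safety review may be triggered at any time if any of the following occur" | Optional; the single-patient trigger needs 21 days without recovery | No automatic hold |
| 9.2: sponsor termination | Discretionary | Discretionary |

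**3. Delay to the review.** Inputs: C2D1 is nominal Day 29, ±2 days (Table 2); the review may follow up to 14 days after the run-in (synopsis). L, the days from subject 1's first dose to subject 3's first dose, is not in the documents and is assumed. Put the event at subject 1's first dose, day 0.

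- Subject 3's C2D1: L + (29 − 1) = L + 28.
- Latest review by the synopsis: L + 28 + 14 = L + 42.

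| L (assumed) | Days from event to review |
|---|---|
| 0 | 28 to 42 |
| 28 | 56 to 70 |
| 56 (one subject per cycle) | 84 to 98 |

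An event e days later shortens each figure by e.

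**4. Infusions before the review.** Cycle 1 has 4 infusions (Days 1, 8, 15 and 22). With C2D1 that makes 4 + 1 = 5 of the 9 planned, or 56%. These are the infusions that a start hold would move to after the panel's report:

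| Run-in subjects not yet started | Cycle 1 only | With C2D1 |
|---|---|---|
| 2 | 2 × 4 = 8 | 2 × 5 = 10 |
| 1 | 4 | 5 |
| 0 | 0 | 0 |

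The count is slightly low under a stagger. If subject 2 starts on day 28 and subject 3 on day 56, subject 2 reaches C3D1 (Day 57) on day 28 + 56 = 84, the day of subject 3's C2D1. Subject 2 would then have had 6 infusions, and the total would be 6 + 5 = 11.

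**How often this could arise.** The documents give no rate for grade 4/5 reactions. For an assumed rate p per subject, the chance of at least one in the first two subjects is 1 − (1 − p)²: 9.8% for p = 5%, 19% for 10%, 36% for 20% and 51% for 30%.

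**The case against.** The strongest reply is that nothing forbids an earlier meeting. Section 6.3 refers to a panel charter that is not among the documents and might contain an earlier trigger. Investigators are expected to act at once for subject safety even if that departs from the protocol (13.3.1), changes to remove an immediate hazard need no prior approval (13.1), and serious events are passed on to investigators as local rules require (10.8.10). Parts of section 9.1 are worded to apply at any time. The drug is not new to humans: 91 myeloma subjects had received it, up to 16 mg/kg, without a maximum tolerated dose being reached (4.2). One review on complete Cycle 1 data is a recognizable design. Amendment 2 also records that the US regulator asked for changes to sections 6.3 and 9.1.

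Much of this is true, and it limits the weight of the point. It does not close the gap. The general powers are discretionary, and the only timing that the protocol states for the compulsory review points the other way. The regulator's recorded requests named the panel in 6.3 and tightened the triggers in 9.1; they do not show agreement with the run-in timing.

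The objections to the size also stand in part. L is assumed, and an event at the first dose is the longest case. L + 28 is not a strict floor, because observation can end early for toxicity. L + 42 is not a ceiling, because replacing a run-in subject extends the run-in. If all three are already on treatment, a start hold saves no infusions and only the earlier meeting helps.

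Finally, the SAP's document history for version 4.0 (November 2021) says that all patients had a post-baseline assessment, so the run-in was over by then. The point therefore concerns the plan as written and any reuse of this run-in text.

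**Conclusion.** The concern holds. Following the protocol to the letter, a grade 4/5 drug reaction in run-in subject 1 or 2 does not require the panel to meet until after subject 3's C2D1, and no rule holds the first dose of a run-in subject who has not started. The delay is about 28-42 days if all three start together and 84-98 days at one subject per cycle. The avoidable exposure is about 8 to 10 infusions with two unstarted subjects, 4 to 5 with one, and none if both others are already on treatment. These figures rest on nominal visit days, an event at subject 1's first dose, and assumed values of L. The charter could soften the conclusion, but a binding protection for subjects belongs in the protocol. This should be fixed as a cheap improvement in subject safety; it does not undermine the trial's analyses.

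**What to change.** In Protocol section 6.3 and the synopsis:

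1. Add a sentence that the Safety Review Panel convenes promptly when the first grade 4/5 drug reaction in the run-in is reported.
2. Add a sentence that run-in subjects who have not had a first dose are not dosed until the panel has reported.
3. To the sentence on run-in subjects continuing, add the exception *unless the panel decides otherwise*, so that the panel rules on subjects already on treatment.
4. Keep the evaluation after subject 3's C2D1 as the end-of-run-in review.

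Align SAP section 6.4.1 for consistency only, since it is the protocol text that protects subjects. The cost is two sentences and one short exception, possibly one extra panel call, and a short delay in the run-in if a reaction occurs.
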